#### **6.2.2.2 Management of hyperlipidemia and hyperglycemia**

Treatment of hyperlipidemia should take into account the pre-treatment status and dietary habits. Grade 2 or higher hypercholesterolemia ( $>300$  mg/dL or  $7.75$  mmol/L) or grade 2 hypertriglyceridemia or higher ( $>2.5$  times upper normal limit) should be treated with a 3-hydroxy-3-methyl-glutaryl (HMG)-CoA reductase inhibitor (e.g., atorvastatin, pravastatin, fluvastatin) or appropriate triglyceride-lowering medication, in addition to diet.

**Note:** Concomitant therapy with fibrates and an HMG-CoA reductase inhibitor is associated with an increased risk of a rare but serious skeletal muscle toxicity manifested by rhabdomyolysis, markedly elevated creatinine phosphokinase (CPK) levels and myoglobinuria, acute renal failure and sometimes death. The risk versus benefit of using this therapy should be determined for individual patients based on their risk of cardiovascular complications of hyperlipidemia.

Hyperglycemia has been reported in patients taking everolimus. Monitoring of fasting serum glucose is recommended prior to the start of everolimus therapy and periodically thereafter. More frequent monitoring is recommended when everolimus is co-administered with other drugs that may induce hyperglycemia. Optimal glycemic control should be achieved before starting trial therapy.

#### **6.2.2.3 Management of hepatitis reactivation**

Monitoring and prophylactic treatment for hepatitis B reactivation

**Table 6-6** provides details of monitoring and prophylactic therapy according to the baseline results of viral load and serologic markers testing.

**Table 6-6 Action to be taken for positive baseline hepatitis B results**

Test	Result	Result	Result	Result	Result
HBV-DNA	+	+ or -	-	-	-
HBs Ag	+ or -	+	-	-	-
HBsAb	+ or -	+ or -	+ and no prior HBV vaccination	+ or -	- or + with prior HBV vaccination
HBc Ab	+ or -	+ or -	+ or -	+	-
Recommendation	Prophylaxis treatment should be started 1-2 weeks prior to first dose of study treatment Monitor HBV-DNA approximately every 4-8 weeks		No prophylaxis Monitor HBV-DNA approximately every 3-4 weeks		No specific action

Antiviral prophylaxis therapy should continue for at least 4 weeks after last dose of study treatment.

For hepatitis B reactivation definition and the management guidelines, see [Table 6-7](#) Guidelines for management of hepatitis B.

**Table 6-7 Guidelines for management of hepatitis B reactivation**

HBV reactivation (with or without clinical signs and symptoms)*	
For patients with baseline results: Positive HBV-DNA OR positive HBs Ag	Treat: Start a second antiviral AND Interrupt study drug administration until resolution: ≤ baseline HBV-DNA levels If resolution occurs within ≤ 28 days study drug should be re-started at one dose lower, if available. (see Table 6-10 – Study drug dose reductions) If the patient is already receiving the lowest dose of study drug according to the protocol, the patient should restart at the same dose after resolution. Both antiviral therapies should continue at least 4 weeks after last dose of study treatment. If resolution occurs > 28 days Patients should discontinue study drug but continue both antiviral therapies at least 4 weeks after last dose of study treatment.
reactivation is defined as: [Increase of 1 log in HBV-DNA relative to baseline HBV-DNA value OR new appearance of measurable HBV-DNA]	
For patients with baseline results: Negative HBV-DNA and HBsAg AND [Positive HBs Ab (with no prior history of vaccination against HBV), OR positive HBc Ab]	Treat: Start first antiviral medication AND Interrupt study treatment administration until resolution: ≤ undetectable (negative) HBV-DNA levels If resolution occurs within ≤ 28 days study drug should be re-started at one dose lower, if available. (see Table 6-10 – Study drug dose reductions) If the patient is already receiving the lowest dose of either study treatment according to the protocol, the patient should restart at the same dose after resolution. Antiviral therapy should continue at least 4 weeks after last dose of study treatment. If resolution occurs > 28 days Patients should discontinue study drug but continue antiviral therapy at least 4 weeks after last dose of study treatment.
reactivation is defined as: New appearance of measurable HBV-DNA	

\* All reactivations of hepatitis B are to be recorded as grade 3 (CTCAE v 4.0 Metabolic Laboratory/Other: Viral Re-activation), unless considered life threatening by the investigator; in which case they should be recorded as grade 4 (CTCAE v 4.0 Metabolic Laboratory/Other: Viral Re-activation). Date of viral reactivation is the date on which the rise or reappearance of HBV-DNA was recorded.

## Monitoring for hepatitis C

The following two categories of patients should be monitored every 4–8 weeks for HCV reactivation:

- Patients with detectable HCV RNA-PCR test at baseline.
- Patients known to have a history of HCV infection, despite a negative viral load test at baseline (including those that were treated and are considered ‘cured’)

For definition of hepatitis C reactivation and the management guidelines, see [Table 6-8](#) Guidelines for management of hepatitis C.

**Table 6-8 Guidelines for management of hepatitis C flare**

HCV reactivation*	
For patients with baseline results: Detectable HCV-RNA HCV flare definition: $>2 \log_{10}$ IU/mL increase in HCV-RNA AND ALT elevation $\times 5$ ULN or $3 \times$ baseline level, whichever is higher.	Discontinue study treatment
For patients with baseline results: Knowledge of past hepatitis C infection with no detectable HCV-RNA HCV flare definition: New appearance of detectable HCV-RNA AND ALT elevation $>5 \times$ ULN or $3 \times$ baseline level, whichever is higher.	Discontinue study treatment

\* All reactivations of hepatitis C are to be recorded as grade 3 (CTCAE v 4.0 Metabolic Laboratory/Other: Viral Re-activation), unless considered life threatening by the investigator; in which case they should be recorded as grade 4 (CTCAE v 4.0 Metabolic Laboratory/Other: Viral Re-activation). Date of viral flare is the date on which both the clinical criteria described above were met. (e.g., for a patients whose HCV-RNA increased by 2 logs on 01JAN2011 and whose ALT reached  $>5 \times$  ULN on 22JAN2011, the date of viral flare is 22JAN2011).

#### **6.2.2.4 Management of diarrhea**

Appearance of grade 1-2 diarrhea attributed to study drug toxicity may be treated with supportive care such as loperamide, initiated at the earliest onset (e.g., 4mg orally followed by 2mg orally every 2 hours until resolution of diarrhea).

#### **6.2.2.5 Management of non-infectious pneumonitis**

Non-infectious pneumonitis is a class effect of rapamycin derivatives. Cases of non-infectious pneumonitis (including interstitial lung disease) have also been described in patients taking everolimus. Some of these have been severe and on rare occasions, a fatal outcome was observed.

A diagnosis of non-infectious pneumonitis should be considered in patients presenting with non-specific respiratory signs and symptoms such as hypoxia, pleural effusion, cough or dyspnea, and in whom infectious, neoplastic and other non-medicinal causes have been excluded by means of appropriate investigations. Opportunistic infections such as pneumocystis jiroveci pneumonia (PJP) should be ruled out in the differential diagnosis of non-infectious pneumonitis. Patients should be advised to report promptly any new or worsening respiratory symptoms.

Patients who develop radiological changes suggestive of non-infectious pneumonitis and have few or no symptoms may continue everolimus therapy without dose alteration.

If symptoms are moderate (grade 2), consideration should be given to interruption of therapy until symptoms improve. The use of corticosteroids may be indicated. Everolimus may be reintroduced at a daily dose approximately 50% lower than the dose previously administered.

For cases of grade 3 non-infectious pneumonitis, interrupt everolimus until resolution to less than or equal to grade 1. Everolimus may be re-initiated at a daily dose approximately 50% lower than the dose previously administered depending on the individual clinical circumstances. If toxicity recurs at grade 3, consider discontinuation of everolimus. For cases of grade 4 noninfectious pneumonitis, everolimus therapy should be discontinued. Corticosteroids may be indicated until clinical symptoms resolve.

For patients who require use of corticosteroids for treatment of non-infectious pneumonitis, prophylaxis for PJP may be considered.

Individuals participating in this trial will be routinely questioned as to the presence of new or changed pulmonary symptoms consistent with lung toxicity. Moreover, potential lung radiological changes can be detected by chest CT/MRI scans that are performed on all patients every 8 weeks for tumor assessments according to the schedule of visits ([Table 7-1](#)). In addition, PFTs will be conducted, including spirometry, DLCO, and room air O2 saturation at rest should be performed. Bronchoscopy with biopsy and/or bronchoalveolar lavage (BAL), if clinically indicated to monitor for pneumonitis. If non-infectious pneumonitis develops, the guidelines in [Table 6-10](#) should be followed. Dose modification instructions are also provided in [Table 6-9](#). Consultation with a pulmonologist is recommended for any case of pneumonitis that develops during the study.

#### **6.2.2.6 Management of infections**

Everolimus has immunosuppressive properties and may predispose patients to bacterial, fungal, viral or protozoan infections, including infections with opportunistic pathogens.

Localized and systemic infections, including pneumonia, other bacterial infections, invasive fungal infections, such as aspergillosis or candidiasis, PJP and viral infections including reactivation of hepatitis B virus, have been described in patients taking everolimus. Some of these infections have been severe (e.g. leading to respiratory or hepatic failure) and occasionally have had a fatal outcome. Physicians and patients should be aware of the increased risk of infection with everolimus. Treat pre-existing infections prior to starting treatment with everolimus. While taking everolimus, be vigilant for symptoms and signs of infection; if a diagnosis of infection is made, institute appropriate treatment promptly and consider interruption or discontinuation of everolimus. If a diagnosis of invasive systemic fungal infection is made, discontinue everolimus and treat with appropriate antifungal therapy.

Patients with positive results of HBV-DNA and/or HBsAg at screening should begin a prophylaxis treatment for 1-2 week prior to beginning everolimus therapy. Patients should have HBV-DNA monitored frequently throughout the course of everolimus therapy for signs of hepatitis reactivation.

Cases of PJP, some with fatal outcome, have been reported in patients who received everolimus. PJP may be associated with concomitant use of corticosteroids or other immunosuppressive agents. Prophylaxis for PJP should be considered when concomitant use of corticosteroids or other immunosuppressive agents is required.

#### **6.2.2.7 Management of hematologic toxicities**

Patients' blood counts should be monitored regularly during treatment. Please refer to [Table 6-11](#) for details.

#### **6.2.2.8 Management of skin toxicity**

For patients with grade 1 toxicity, no specific supportive care is usually needed or indicated. Rash must be reported as an AE. Patients with grade 2 or higher toxicity may be treated with the following suggested supportive measures at the discretion of the investigator: oral minocycline, topical tetracycline, topical clindamycin, topical silver sulfadiazine, diphenhydramine, oral prednisolone (short course) topical corticosteroids or pimecrolimus.

#### **6.2.2.9 Follow up for toxicities**

Patients whose treatment is interrupted or permanently discontinued due to an adverse event or abnormal laboratory value must be followed at least weekly until resolution or stabilization of the event, whichever comes first. The patient must be discontinued from the study if they require a dose delay of  $\geq 28$  days.

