## Glossary of terms

Assessment	A procedure used to generate data required by the study
Cohort	A group of newly enrolled patients treated at a specific dose and regimen (i.e. treatment group) at the same time
Cycles	Number and timing or recommended repetitions of therapy are usually expressed as number of days (e.g.: q28 days)
Dose level	The dose of drug given to the patient (total daily or weekly etc.)
Enrollment	Point/time of patient entry into the study; the point at which informed consent must be obtained (i.e. prior to starting any of the procedures described in the protocol)
First line setting	Everolimus plus letrozole as first line treatment for patients with metastatic or locally advanced unresectable breast cancer
Second line setting	Everolimus plus exemestane treatment following progression on first line therapy with everolimus plus letrozole
Investigational drug	The study treatment whose properties are being tested in the study; this definition is consistent with US CFR 21 Section 312.3 and is synonymous with "investigational new drug."
Investigational treatment	Drug whose properties are being tested in the study as well as their associated placebo and active treatment controls (when applicable). This also includes approved drugs used outside of their indication/approved dosage, or that are tested in a fixed combination. Investigational treatment generally does not include other study treatments administered as concomitant background therapy required or allowed by the protocol when used in within approved indication/dosage
Medication number	A unique identifier on the label of each study treatment package which is linked to one of the treatment groups of a study
Other study treatment	Any drug administered to the patient as part of the required study procedures that was not included in the investigational treatment
Patient No.	A unique identifying number assigned to each patient/subject/healthy volunteer who enrolls in the study
Period	A subdivision of the study timeline; divides stages into smaller functional segments such as screening, baseline, titration, washout, etc.
Premature patient withdrawal	Point/time when the patient exits from the study prior to the planned completion of all study treatment administration and/or assessments; at this time all study treatment administration is discontinued and no further assessments are planned, unless the patient will be followed for progression and/or survival

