**Table 6-11 Dosing guidelines for study drug-related hematologic toxicities**

Adverse event	Severity 	Everolimus Dose Adjustment
Platelet count decreased (Thrombocytopenia)	Grade 1 (<LLN-75.0x10  /L)	No dose adjustment required.
	Grade 2 (<75.0-50.0x10  /L)	Temporary dose interruption until recovery to Grade $\leq$ 1. Re-initiate everolimus at the same dose.
	Grade 3 (<50.0-25.0x10  /L)	Temporary dose interruption until recovery to Grade $\leq$ 1. Re-initiate everolimus at a lower dose.
	Grade 4 (<25.0x10  /L)	Temporary dose interruption until recovery to Grade $\leq$ 1. Re-initiate everolimus at a lower dose.
Neutrophil count decreased (Neutropenia)	Grade 1 (<LLN-1.5x10  /L)	No dose adjustment required.
	Grade 2 (<1.5-1.0x10  /L)	No dose adjustment required.
	Grade 3 (<1.0-0.5x10  /L)	Temporary dose interruption until recovery to Grade $\leq$ 2 (ANC $\geq$ 1.0x10  /L). Re-initiate everolimus at the same dose.
	Grade 4 (<0.5x10  /L)	Temporary dose interruption until recovery to Grade $\leq$ 2 (ANC $\geq$ 1.0x10  /L). Re-initiate everolimus at a lower dose.
Febrile neutropenia	Grade 3 (ANC <1.0x10  /L with single temperature $>$ 38.3° C (101°F) or sustained temperature $\geq$ 38°C (100.4°F) for $>$ 1h)	Temporary dose interruption until recovery to Grade $\leq$ 2 (ANC $\geq$ 1.25x10  /L) and no fever. Re-initiate everolimus at a lower dose.
	Grade 4 (Life-threatening consequences; urgent intervention indicated)	Discontinue everolimus.
Any hematologic toxicity requiring study drug interruption for $>$ 28 days		Discontinue everolimus.

 Grading based on National Cancer Institute (NCI) Common Terminology Criteria for Adverse Events (CTCAE) v4.03

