### **7.1.5 End of treatment visit including study completion and premature withdrawal**

At the time patients discontinue study treatment (in the first line treatment or, if applicable, second line treatment and Extension Phase), a visit should be scheduled as soon as possible (within 2 weeks), at which time all of the assessments listed for the End of Treatment (EOT) visit will be performed. An End of Treatment eCRF page should be completed separately for both first and second line treatment for the core study phase, and an End of Treatment eCRF for the Extension Phase should be completed for those subjects ending treatment while in the Extension Phase. The EOT eCRF will provide the date and reason for stopping the study treatment.

[figure not shown]
If patients refuse to return for an end of treatment visit or are unable to do so, every effort should be made to contact them or a knowledgeable informant by telephone to determine the primary reason for premature withdrawal from the study and record this information on the End of Treatment eCRF page.

Patients may voluntarily withdraw from the study or be dropped from it at the discretion of the investigator at any time. Patients may be withdrawn from the study if any of the following occur:

- Pregnancy
- Discovery of patient ineligibility
- Protocol violation or errors in treatment compliance [study treatment, other prescribed or non-prescribed medications]
- Missed/unscheduled/off-schedule/incomplete/incorrect assessments
- Adverse events (including abnormal laboratory value, abnormal test procedure result)
- Unacceptable toxicity
- Subject withdrew consent
- Lost to follow up
- Administrative problems
- Death
- New cancer therapy
- Disease progression
- Treatment duration completed as per protocol
- Discontinuation of everolimus development by Novartis

At a minimum, all patients who discontinue study treatment for any reason, including those who refuse to return for a final visit, will be contacted for safety evaluations during the 28 days following the last dose of study treatment. If patients begin second line treatment < 28 days after completion of first line treatment, safety evaluations should continue until second line treatment begins.

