## 7.2 Assessment types

### 7.2.1 Efficacy assessments

#### Core Phase

Patients should have either at least one lesion that can be measured as per RECIST 1.0 criteria OR have bone lesions: lytic or mixed (lytic + sclerotic) in the absence of measurable disease as defined above.

For patients with measurable disease at baseline (as per RECIST 1.0 criteria), efficacy (overall tumor response and progression) will be evaluated every 8 weeks (+/- 1 week) during the Core Phase according to the RECIST 1.0 criteria. If an initial observation of response is made, a confirmation scan (or photography for measurable skin lesions) should be obtained at least 4 weeks after the initial observation. All patients being discontinued from the study for disease progression must have their progression documented using the criteria specified in [Appendix 2](#). All patients who discontinue study treatment for any reason (i.e., an adverse event, administrative reasons etc) other than disease progression or consent withdrawal will continue to have tumor assessments per the schedule during the Core Phase until disease progression or until new anti-cancer therapy is initiated.

All primary and secondary endpoints based on radiological (and photographic when applicable) assessments of tumor burden will be derived using the local (treating centers) radiologist's / investigator's assessment.

A bone scan or a skeletal survey should be performed at baseline for all patients within 28 days of enrollment. Any abnormalities (i.e., hotspots) identified on the bone scan must be confirmed by X-ray, CT scan with bone windows or MRI. Bone lesions identified at baseline should follow the same assessment schedule as for measurable lesions. Additional bone scans or skeletal surveys should be performed if clinically indicated. Abnormalities found on subsequent bone scans must also be confirmed by X-ray, CT scan or MRI.

The same method of assessment and the same technique should be used to characterize each identified and reported lesion at baseline for each study tumor assessment after start of study treatment.

If possible, each center should have a designated radiologist responsible for the interpretation of CT or MRI scans and the evaluation according to RECIST 1.0 criteria (see [Appendix 2](#) for details). The same radiologist/physician should perform the evaluation for the entire duration of the study. All radiology evaluations will be performed initially by the local radiologist.

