#### **14.2.21 Treatment and study completion CRFs**

If study drug is discontinued, the **treatment completion page** is to be completed with a visit date reflecting the date the discontinuation decision was made, and with the 'Last known date subject took study drug' and one of the following reasons:

- Adverse event(s)
- Abnormal laboratory value(s)
- Abnormal test procedure results(s)
- Protocol violation
- Subject withdrew consent
- Lost to follow-up
- Administrative problems
- Death
- Disease progression
- Treatment duration completed as per protocol (optional, to be used if only a fixed number of cycles is given)

For reasons other than progression (and death) it should be checked if this was not in fact progression (especially reasons Adverse Events, Abnormal laboratory value (s), Abnormal test procedure result and subject withdrew consent). Also it should be checked if patient withdrew consent because of safety issues, in which case reasons Adverse Events, Abnormal laboratory value (s), Abnormal test procedure result should be used.

All patients who discontinued study drug for reasons other than documented progression, death or lost to follow-up will be followed for progression thereafter (patients who withdrew consent might not be followed with regular tumor assessments at the study site, but should ideally be followed until progression outside the study site). Ideally, all patients who discontinued study drug for progression without documented progression will still be followed with regular tumor assessments (e.g. in case of central radiology review). During that evaluation period, usually only tumor measurements (and/or response status) and survival data are collected. In some protocols, the subsequent anti-cancer therapies may also be recorded.

At the end of the study evaluation period, the **study evaluation completion page** is filled out with the following options:

- Subject withdrew consent
- Lost to follow-up

- Administrative problems (when follow-up for progression has met protocol required events, e.g. follow-up stopped at certain number of events or certain time)
- Death
- New cancer therapy (optional, to be used when follow-up for progression is stopped in this case)
- Disease progression

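### Section 6.2.2.9 requires discontinuation from the study after a 28-day dose delay and does not preserve the tumour and survival follow-up required elsewhere, on which the primary PFS analysis depends

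*Protocol*

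**What the plan says.** **Leaving the study.** Section 6.2.2.9: "The patient must be discontinued from the study if they require a dose delay of" 28 days or more. The sentence is mandatory, names the study rather than the treatment, and makes no exception for tumour or survival follow-up. The only follow-up that section sets is at least weekly review until the toxicity resolves or stabilises. Section 7.1.5 introduces a list with "Patients may be withdrawn from the study if any of the following occur". Its entries include adverse events, "Unacceptable toxicity", discovery of ineligibility and "Missed/unscheduled/off-schedule/incomplete/incorrect assessments".

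**Continuing follow-up.** Section 7.2.1 (Core Phase) says that those whose treatment ends on grounds "other than disease progression or consent withdrawal will continue to have tumor assessments per the schedule during the Core Phase until disease progression". Starting a new anti-cancer therapy also ends the schedule. Appendix 2, Section 14.2.21, agrees: "All patients who discontinued study drug for reasons other than documented progression, death or lost to follow-up will be followed for progression thereafter". Sections 4.1 and 7.1.6.2 require survival follow-up after treatment stops.

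**Definitions.** The glossary separates stopping study treatment from premature withdrawal. After the latter, "no further assessments are planned, unless the patient will be followed for progression and/or survival".

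**Related 28-day provisions.** Table 6-11 covers "Any hematologic toxicity requiring study drug interruption for" more than 28 days, and its consequence is stopping everolimus. Table 6-7 (hepatitis B reactivation) provides for restarting study drug if resolution occurs within 28 days, and for stopping study drug if it takes longer.

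**Censoring.** Section 10.4.3 censors patients without a PFS event at the last adequate tumour assessment. It also censors an event seen after two or more missing or inadequate assessments.

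**The concern.** The primary result is a Kaplan-Meier median PFS from a single arm, so no comparator exists against which a follow-up bias might cancel. If a site treats a long dose delay as exit from the study, scans stop and the patient is censored early. Survival follow-up would not fully rescue PFS. With scans due every 8 weeks, a death or progression learned of after two missed assessments is censored back to the last evaluable scan.

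Two things are then at stake. Events are lost, which widens the confidence interval on which the sample size is justified. And if patients who leave for toxicity or poor attendance differ in prognosis from those who stay, the censoring is informative and the median is biased. Exit for ineligibility raises a further point. The Full Analysis Set is everyone assigned first-line treatment, so ending follow-up on discovering ineligibility would leave members of that set unobserved.

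**Working it through.** **1. The passages side by side**

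| Place | Trigger | Consequence | Force |
|---|---|---|---|
| 6.2.2.9 | dose delay of 28 days or more | off the study | must |
| 7.1.5 list | toxicity, ineligibility, missed assessments and others | off the study | may |
| Table 6-11 | haematologic interruption over 28 days | off everolimus | directive |
| Table 6-7 | hepatitis B resolution over 28 days | off study drug | should |
| 7.2.1 | treatment stopped, not for progression or consent withdrawal | scans continue | will |
| 14.2.21 | drug stopped, not for progression, death or loss to follow-up | followed for progression | will |

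At a delay of exactly 28 days, 6.2.2.9 applies, Table 6-11 does not, and Table 6-7 still provides for restarting. The consequence also differs: the study in one place, the drug in the others.

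**2. The plan's own precision table**

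Inputs from Section 10.8: N = 200, accrual A = 18 months, follow-up F = 12 months, 10% lost to follow-up, medians m of 11 to 14 months. Assumed: exponential PFS, uniform accrual and exponential loss, with 10% spread over the 30-month study.

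- λ = ln 2 / m, η = −ln(0.9)/30, t = λ + η
- Events d = N·(λ/t)·[1 − (e^(−tF) − e^(−t(A+F)))/(tA)]
- 95% CI = m·exp(±1.96/√d)

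For m = 12: λ = 0.05776, η = 0.00351, t = 0.06127. So d = 200 × 0.9427 × [1 − (0.4794 − 0.1591)/1.1029] = 133.8. The half-width on the log scale is 1.96/√133.8 = 0.1694, giving 10.13 to 14.22, width 4.09.

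| Median | Events | Recomputed CI (width) | Stated CI (width) |
|---|---|---|---|
| 11 | 139.7 | 9.32-12.98 (3.66) | 9.32-12.98 (3.66) |
| 12 | 133.8 | 10.13-14.22 (4.09) | 10.13-14.22 (4.09) |
| 13 | 128.2 | 10.93-15.46 (4.52) | 10.93-15.46 (4.53) |
| 14 | 123.1 | 11.73-16.71 (4.97) | 11.73-16.71 (4.98) |

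The table reproduces to within 0.01 month.

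**3. Loss of precision (assumed exit rates)**

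The protocol gives no rate of exit under these provisions. Suppose a further 10% or 20% leave early and contribute no events, at a 12-month median:

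- 10%: d = 133.8 × 0.9 = 120.4; width = 12·(e^h − e^(−h)) with h = 1.96/√120.4 = 0.1786, giving 4.31 months.
- 20%: d = 133.8 × 0.8 = 107.0; h = 0.1894, giving 4.57 months.

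**4. Possible bias (assumed exit rates and hazards)**

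This is a large simulation with 12 to 30 months of potential follow-up and no other loss. Patients who stay have a median of 12 months. Patients marked to leave do so uniformly between months 1 and 6, unless they progress first, and have the stated hazard ratio throughout.

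| Marked to leave | Hazard ratio | Median if followed | Median if taken off study | Difference |
|---|---|---|---|---|
| 10% | 1 | 12.00 | 12.00 | 0.00 |
| 10% | 1.5 | 11.46 | 11.79 | 0.33 |
| 10% | 2 | 11.15 | 11.67 | 0.52 |
| 20% | 1 | 12.00 | 11.99 | −0.01 |
| 20% | 1.5 | 10.99 | 11.62 | 0.63 |
| 20% | 2 | 10.35 | 11.33 | 0.98 |

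**The case against.** A reader might infer that the two sets of rules cannot both be followed. The documents do not go that far. The glossary lets a prematurely withdrawn patient still be followed for progression or survival, Section 7.2.1 supplies that follow-up for all who stop treatment, and Tables 7-1 and 7-2 have a post-treatment evaluation column. A careful site could comply with everything. What stands is that neither 6.2.2.9 nor the 7.1.5 list refers to the exception, so the outcome depends on which section a site reads.

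A reader might also infer that 7.1.5 itself takes patients off the study. It permits this but does not require it. Its list includes disease progression and completion of treatment per protocol, and Sections 4.1, 6.1.2 and 7.1.2 cite it for reasons to stop treatment. It also asks for end-of-treatment imaging when treatment stops without progression, unless the last imaging was within 4 weeks. This is mainly loose wording, and 6.2.2.9 is the stronger half of the point.

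Third, nothing in the protocol shows that those who leave progress faster, and some of them may already fall within the 10% loss assumed in Section 10.8. Both objections are sound, and they are why the month figures are illustrations only. The difference between 28 days or more and more than 28 days matters only at exactly 28 days.

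Finally, the last patient entered on 17-Dec-2014, primary PFS was planned 12 months later, and this version is dated 14-Feb-2017. Rewording cannot recover scans already missed.

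**Conclusion.** The point holds as an inconsistency in the current text with a route to the primary endpoint. Section 6.2.2.9 mandates exit from the study where 7.2.1 and Appendix 2 expect tumour assessments to continue, and where Tables 6-7 and 6-11 speak only of the drug. Read literally, it ends scans and censors PFS early under 10.4.3.

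The size is not derivable from the document. If 10-20% left early and had 1.5-2 times the hazard, the median would be overstated by about 0.3-1.0 month, against the 2 to 5 month gain over 9 months that Section 10.8 anticipates. With equal hazard there is no bias, and the interval at a 12-month median widens from 4.09 to about 4.3-4.6 months. Both illustrations assume that every affected patient stops being scanned. They do not show that the trial's median is in fact biased.

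**What to change.** - In 6.2.2.9 and 7.1.5, state that in the Core Phase, whatever treatment-stopping rule applies, stopping treatment does not end follow-up. This includes stopping for a dose delay, toxicity, ineligibility or missed assessments. Tumour assessments continue under 7.2.1 until progression or new anti-cancer therapy, and survival follow-up continues under 7.1.6.2, unless consent is withdrawn.
- Limit this to the Core Phase. Scheduled imaging is not required in the Extension Phase, and patients completing that phase are not followed for survival.
- The sponsor must reconcile the boundaries and consequences in 6.2.2.9, Table 6-7 and Table 6-11. No stopping rule is proposed here.
- For data already collected, identify patients whose tumour assessments ended under these provisions and report them in the PFS censoring summary.

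The wording costs little, because 7.2.1 already requires the visits. The remaining cost is a review of study exits; assessments already missed cannot be recovered.
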